10.4.1.4 AEs requiring specific monitoring and reporting on specific e-CRFs

The following AEs require specific monitoring and should be reported on the specific e-CRF for completion. These AEs will only qualify for expedited reporting when Serious (fulfilling SAE criteria).

- Suspected allergic reactions (please refer to [Section 10.6.3](#));
- Monitoring of patients with increased pancreatic enzymes $>2 \times$ ULN/pancreatic events (please refer to [Section 10.6.4](#));
- Monitoring of patients with increased calcitonin ≥ 20 pg/ mL (please refer to [Section 10.6.5](#));
- Monitoring of device-related events (please refer to [Section 10.6.8](#)).

10.4.2 General guidelines for reporting adverse events

- All AEs, regardless of seriousness or relationship to IMP/NIMP, spanning from the signature of the informed consent form until the end of the study as defined by the protocol for that patient, are to be recorded on the corresponding screen(s) of the e-CRF.
- Whenever possible, diagnosis or single syndrome should be reported instead of symptoms. The Investigator should specify the date of onset, intensity, action taken with respect to IMP, corrective treatment/therapy given, additional investigations performed, outcome, and his/her opinion as to whether there is a reasonable possibility that the AE was caused by the IMP or by the study procedure(s).
- The Investigator should take appropriate measures to follow all AEs until clinical recovery is complete and laboratory results have returned to normal, or until progression has been stabilized, or until death, in order to ensure the safety of the patients. This may imply that observations will continue beyond the last planned visit per protocol, and that additional investigations may be requested by the monitoring team up to as noticed by the Sponsor.
- When treatment is prematurely discontinued, the patient's observations will continue until the end of the study as defined by the protocol for that patient.
- Laboratory, vital signs or ECG abnormalities are to be recorded as AEs only if:
 - Symptomatic and/or;
 - Requiring either corrective treatment or consultation, and/or;
 - Leading to IMP discontinuation or modification of dosing, and/or;
 - Fulfilling a seriousness criterion, and/or;
 - Defined as an AESI or event requiring specific monitoring.

10.4.3 Instructions for reporting serious adverse events

In the case of occurrence of an SAE, the Investigator or any designees must immediately:

- ENTER (within 24 hours) the information related to the SAE in the appropriate screens of the e-CRF; the system will automatically send a notification to the monitoring team after approval of the Investigator within the e-CRF or after a standard delay.
- SEND (preferably by fax or e-mail) a photocopy of all examinations carried out and the dates on which these examinations were performed, to the representative of the monitoring team whose name, fax number, and email address appear on the clinical trial protocol. Care should be taken to ensure that the patient's identity is protected and the patient's identifiers in the clinical trial are properly mentioned on any copy of a source document provided to the Sponsor. For laboratory results, include the laboratory normal ranges.
- All further data updates should be recorded in the e-CRF as appropriate, and further documentation as well as additional information (for laboratory data, concomitant medications, patient status, etc) should be sent (by fax or e-mail) to the monitoring team within 24 hours of knowledge of the SAE. In addition, every effort should be made to further document any SAE that is fatal or life threatening within a week (7 days) of the initial notification.
- A back-up plan (using a paper CRF process) is available and should be used when the e-CRF system does not work (please see [Appendix C](#)).

Any SAE brought to the attention of the Investigator at any time after the end of the study for the patient and considered by him/her to be caused by the IMP with a reasonable possibility, should be reported to the monitoring team.

10.4.4 Guidelines for reporting adverse events of special interest

For AESIs, the Sponsor must be informed immediately (ie, within 24 hours), as per SAE notification guidelines described in [Section 10.4.1.3](#), even if not fulfilling a seriousness criterion, using the corresponding pages of the CRF (to be sent) or screens in the e-CRF.

Instructions for AE reporting are summarized in [Table 2](#).

10.4.5 Guidelines for management of specific laboratory abnormalities

Decision trees for the management of certain laboratory abnormalities by Sanofi are provided in [Appendix B](#).

The following laboratory abnormalities should be monitored, documented, and managed according to the related flow chart in protocol appendices.

- Neutropenia;
- Thrombocytopenia;
- Increase in ALT;
- Acute renal insufficiency;
- Suspicion of rhabdomyolysis.

Table 2 - Summary of adverse event reporting instructions

Event category	Reporting timeframe	Specific events in this category	Case Report Form completion		
			AE form	Safety complementary form	Other specific forms
Adverse Event (non-SAE, non-AESI)	Routine	Any AE that is not SAE or AESI	Yes	No	No
Serious Adverse Event (non-AESI or AESI)	Expedited (within 24 hours)	Any AE meeting seriousness criterion per Section 10.4.1.2	Yes	Yes	No
Adverse Event of Special Interest	Expedited (within 24 hours)	Pregnancy of female patient	Yes	No	Yes
		Pregnancy of female partner of male patient	Yes	No	Yes
		Symptomatic overdose* with IMP/NIMP	Yes	Yes	No
		Confirmed increase in ALT >3x ULN	Yes	No	Yes
AEs requiring specific monitoring (non-SAEs)	Routine	Suspected allergic reactions	Yes	No	Yes
		Confirmed increase amylase/lipase >2x ULN	Yes	No	Yes
		Confirmed increased calcitonin ≥ 20 pg/mL	Yes	No	Yes
		Device-related events#	Yes	No	Yes
Laboratory, vital signs, ECG abnormality asymptomatic overdose recorded as AE (non-SAE, non-AESI)	Routine	Neutropenia	Yes	No	No
		Thrombocytopenia	Yes	No	No
		Acute renal insufficiency	Yes	No	No
		Suspicion of rhabdomyolysis	Yes	No	No
		Other (eg, leading to IMP discontinuation)	Yes	No	No

Symptomatic hypoglycemia will be reported on the dedicated hypoglycemia event page.

*: Asymptomatic overdose is reported in the AE form and does not require expedited reporting.

#: Only device-related events associated with clinical adverse events will be reported as AE. Please refer to [Section 10.6.8](#).

10.5 OBLIGATIONS OF THE SPONSOR

During the course of the study, the Sponsor will report in an expedited manner:

- All SAEs that are both unexpected and at least reasonably related to the IMP (SUSAR), to the regulatory authorities, Independent Ethics Committees (IECs)/Institutional Review Boards (IRBs) as appropriate and to the Investigators.
- All SAEs that are expected and at least reasonably related to the IMPs to the regulatory authorities, according to local regulations.

Any other AE not listed as an expected event in the lixisenatide/insulin glargine combination product Investigator's Brochure (IB) or the approved labelling referenced in [Section 16](#), ie, EU SmPC for Victoza®, Byetta®, Bydureon®, or Trulicity® or US Prescribing Information for Tanzeum®-will be considered as an unexpected event.

In this study, some AEs considered related to the underlying condition (eg, blood glucose increased) will not be considered unexpected as given in the IB or the approved labelling referenced in the protocol.

The Sponsor will report all safety observations made during the conduct of the trial in the clinical study report (CSR).

10.6 SAFETY INSTRUCTIONS

10.6.1 Symptomatic Hypoglycemia

Symptomatic hypoglycemia events will be categorized as follows:

Severe symptomatic hypoglycemia

Severe symptomatic hypoglycemia is an event requiring assistance of another person to actively administer carbohydrate, glucagon, or other resuscitative actions. These episodes may be associated with sufficient neuroglycopenia to induce seizure, unconsciousness or coma. Plasma glucose measurements may not be available during such an event, but neurological recovery attributable to the restoration of plasma glucose to normal is considered sufficient evidence that the event was induced by a low plasma glucose concentration.

The definition of severe symptomatic hypoglycemia includes all episodes in which neurological impairment was severe enough to prevent self-treatment and which were thus thought to place patients at risk for injury to themselves or others.

Note that “requires assistance” means that the patient could not help himself or herself. Assisting a patient out of kindness, when assistance is not required, should not be considered a “requires assistance” incident.

Severe symptomatic hypoglycemia will be qualified as an SAE only if it fulfills SAE criteria. All events of seizure, unconsciousness or coma must be reported as SAEs.

Documented symptomatic hypoglycemia

Documented symptomatic hypoglycemia is an event during which typical symptoms of hypoglycemia are accompanied by a measured plasma glucose concentration of ≤ 70 mg/dL (3.9 mmol/L).

Clinical symptoms that are considered to result from a hypoglycemic episode can include (but are not limited to): increased sweating, nervousness, asthenia, tremor, dizziness, increased appetite, palpitations, headache, sleep disorder, confusion, seizures, unconsciousness, and coma.

Probable symptomatic hypoglycemia

Probable symptomatic hypoglycemia is an event during which symptoms of hypoglycemia are not accompanied by a plasma glucose determination, but was presumably caused by a plasma glucose concentration less than or equal to 70 mg/dL (3.9 mmol/L); symptoms improved with oral carbohydrate, or Intravenous glucose or glucagon injection without a test of plasma glucose.

Patients will be instructed to measure finger-stick plasma glucose levels prior to the administration of carbohydrates whenever symptomatic hypoglycemia is suspected, unless safety considerations necessitate immediate glucose administration prior to confirmation, and then a glucose measurement should be performed as soon as safe, with appropriate diary documentation. Details on hypoglycemia episodes will be captured in the patient diaries, and patients will contact the sites as soon as possible following severe events to review the details and decide on any necessary measures to be taken.

Symptomatic hypoglycemia episodes will be documented on the dedicated hypoglycemia event page in the e-CRF. Symptomatic hypoglycemia events fulfilling the criteria of a SAE will also be documented on AE and SAE forms in the e-CRF.

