The number (%) of patients with events reported on Device-related event questionnaire will be summarized for each treatment group along with 2 subcategories, events associated with a clinical event (either symptomatic hypoglycemic event or adverse event) and events not associated with clinical event. The number of events and rates in patient year will also be summarized as appropriate. In addition, a listing of patients with those events will be provided.

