- ticked “Subject Treated Self” or “Subject was Capable of Treating Self but Received Assistance” to the question “Countermeasure Administration” and
- ticked at least one “Yes” to the question “Symptoms” and
- with a measured plasma glucose value ≤ 70 mg/dL (3.9 mmol/L).

Probable symptomatic hypoglycemia

Probable symptomatic hypoglycemia is an event during which symptoms of hypoglycemia are not accompanied by a plasma glucose determination, but was presumably caused by a plasma glucose concentration less than or equal to 70 mg/dL (3.9 mmol/L); symptoms treated with oral carbohydrate without a test of plasma glucose.

In the eCRF, probable symptomatic hypoglycemia is identified based on information captured in the “Symptomatic hypoglycemic event information” page as those

- ticked “Subject Treated Self” or “Subject was Capable of Treating Self but Received Assistance” to the question “Countermeasure Administration” and
- ticked at least one “Yes” to the question “Symptoms” and
- ticked “Oral carbohydrate”, “Intravenous glucose” or “Glucagon injection” to the question “Was Any Countermeasure Given for the Hypoglycemic Event?” and
- ticked “Yes” to the question “Did this countermeasure lead a significant improvement or prompt recovery?” and
- with no plasma glucose value,

Symptomatic hypoglycemia events fulfilling the criteria of a SAE will also be recorded on AE and SAE forms in eCRF.

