- All treatment-emergent SAEs by primary SOC, HLGT, HLT, and PT, showing the number (%) of patients with at least 1 treatment-emergent SAE, sorted by the internationally agreed SOC order. The other levels (HLGT, HLT, PT) will be presented in alphabetical order.

- All treatment-emergent SAEs regardless of relationship and related to IMP, by primary SOC, HLGT, HLT, and PT, showing the number (%) of patients with at least 1 treatment-emergent SAEs, sorted by the internationally agreed SOC order. The other levels (HLGT, HLT, PT) will be presented in alphabetical order.

Analysis of all treatment-emergent adverse event(s) leading to treatment discontinuation

- All TEAEs leading to treatment discontinuation, by primary SOC, HLGT, HLT, and PT, showing the number (%) of patients with at least 1 TEAE leading to treatment discontinuation, sorted by the internationally agreed SOC order. The other levels (HLGT, HLT, PT) will be presented in alphabetical order.

Local tolerability at injection site

The number (%) of patients with local intolerability at injection site will be summarized by PT (PTs coded from the investigator reported terms or PTs coded from ARAC diagnosis terms), sorted by decreasing incidence of PT. Similar summaries will be provided for FRC group respectively by anti-lixisenatide and anti-insulin glargine antibody status (Positive, Negative). All events will be listed.

Allergic reactions

Kaplan-Meier curves will be provided for the time to first onset of events adjudicated as allergic reactions by ARAC. The number (%) of patients with events adjudicated as allergic reactions by ARAC will be summarized by PT (sorted by decreasing incidence of PT) and ARAC diagnosis along with 2 subcategories, events adjudicated as possibly related to IMP and events adjudicated as not related to IMP. Tabulation summaries will be provided as necessary by gender (Male, Female), age group (<50, ≥50 to <65, ≥65 to <75, ≥75 years of age), race (American Indian or Alaska Native, Asian/Oriental, Black, Native Hawaiian or Other Pacific Islander, White, Other). Similar summaries will be provided for FRC group respectively by anti-lixisenatide and anti-insulin glargine antibody status (Positive, Negative).

All the allergic events reported by the investigator on the AE form for suspected allergic event and its associated complementary forms (confirmed or not confirmed by ARAC) will be listed.

Pancreatic-related events

- Increased pancreatic enzymes >2 times ULN

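### Non-serious symptomatic hypoglycemia that ends treatment is not required on the AE form, so the table of TEAEs leading to permanent discontinuation may undercount it

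*Protocol*

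**What the plan says.** **Recording.** Protocol 10.6.1 names the usual place for these events: "Symptomatic hypoglycemia episodes will be documented on the dedicated hypoglycemia event page in the e-CRF". The footnote to Table 2 in Protocol 10.4.5, the table that says which events need an AE form, agrees: "Symptomatic hypoglycemia will be reported on the dedicated hypoglycemia event page". The AE form is added for serious events: "Symptomatic hypoglycemia events fulfilling the criteria of a SAE will also be documented on AE and SAE forms in the e-CRF". SAP 2.1.4.1 carries the same rule: "Symptomatic hypoglycemia events fulfilling the criteria of a SAE will also be recorded on AE and SAE forms in eCRF". Severity alone does not trigger it: "Severe symptomatic hypoglycemia will be qualified as an SAE only if it fulfills SAE criteria". Episodes with seizure, unconsciousness or coma must always be reported as SAEs.

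**Discontinuation as a trigger for an AE entry.** Protocol 10.4.2 lists the conditions under which laboratory, vital-sign or ECG abnormalities become AEs. One of them is "Leading to IMP discontinuation or modification of dosing, and/or". Symptomatic hypoglycemia is not named there.

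**Analysis.** Protocol 11.4.6.2 and SAP 2.4.5.2 plan, by arm, an overview line for TEAEs leading to permanent treatment discontinuation and a table described in the SAP as "All TEAEs leading to treatment discontinuation, by primary SOC, HLGT, HLT, and PT". SAP 2.2 plans disposition tables with reasons for stopping treatment, Kaplan-Meier plots of discontinuation for any reason and due to AE, and a patient listing with the reason.

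**The concern.** The number of patients who stop treatment because of an adverse event is one of the first tolerability figures a reader compares between arms. Hypoglycemia is an obvious candidate reason for stopping a product that contains insulin. If it reaches the AE form only when serious, a patient who stops for repeated non-serious episodes may not be counted in that figure. The report could then show one number of discontinuations in the AE table and a different picture in the disposition reasons, with no planned step to explain the difference. Sites could also differ in practice, because the text leaves them to decide whether to make the additional AE entry.

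**Working it through.** No sample size, power or alpha figure is involved. The check follows one hypothetical patient from the recording rules to the planned tables.

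1. **Event.** A patient has symptomatic hypoglycemia that meets no SAE criterion, and study drug is permanently stopped because of it.
2. **Form required.** Protocol 10.6.1 and the Table 2 footnote require the hypoglycemia page. The sentence that adds the AE form is limited to SAEs. The word "also" in "Symptomatic hypoglycemia events fulfilling the criteria of a SAE will also be documented on AE and SAE forms in the e-CRF" has a purpose only if other episodes are not routinely entered there.
3. **Separate streams.** The documents keep the two kinds of event apart elsewhere. Both list hypoglycemia and AEs as separate safety endpoints (Protocol 9.2.2, SAP 2.1.4). Device problems are summarized according to "events associated with a clinical event (either symptomatic hypoglycemic event or adverse event" (Protocol 11.4.6.2). By contrast, injection-site, allergic, pancreatic-enzyme and calcitonin events are each directed to an AE page or form (Protocol 10.6.2 to 10.6.5).
4. **Source of the table.** The discontinuation outputs count TEAEs by MedDRA term. SAP 2.5.3 places the item recording the action taken with study drug on the adverse event page. An event without an AE record has no evident route into these outputs.
5. **Hypoglycemia analyses.** SAP 2.4.5.1 plans counts, rates, subgroups, weekly intervals, time to first event, clock time and a listing. In the text available, none of these counts episodes that ended treatment.
6. **Where the patient still appears.** Protocol 10.3 and 10.3.3 require discontinuations and their reasons to be documented. SAP 2.2 tabulates the reasons and plans the all-reason plot and the listing.

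**Scale.** Planned FRC arm: 250 (Protocol 11.1). For k omitted patients, the FRC percentage falls by k/250 × 100 points.

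| Omitted FRC patients (assumed) | Understatement |
|---|---|
| 0 | 0 points |
| 1 | 1/250 = 0.4 points |
| 3 | 3/250 = 1.2 points |

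The documents give no expected number, so k is purely illustrative. The actual denominator is the safety population, which may differ slightly from 250.

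**The case against.** The strongest reply is that silence is not prohibition. Protocol 10.4.2 asks for all AEs to be recorded whatever their seriousness, and the diary description in Protocol 9.2.1.2.3.2 counts signs and symptoms suggesting hypoglycemia among adverse events. A reader might infer from the SAE sentence that non-serious episodes are barred from the AE form and that these patients are certain to be missing. The documents do not support that: no sentence forbids an entry, and a careful site might make one.

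The further argument, that 10.4.2 already requires the entry when study drug is stopped, does not close the gap. The general rule sends an AE to its corresponding screen, and for hypoglycemia the named screen is the dedicated page. The discontinuation condition covers laboratory, vital-sign and ECG abnormalities only, and whether a self-measured glucose value counts is not stated. Probable hypoglycemia has no glucose value by definition. If the rule did reach symptomatic hypoglycemia, its separate condition for symptomatic abnormalities would put every episode on the AE form, and the SAE sentence would be redundant.

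Other parts of the reply stand:

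- The patients are not lost from the report, because the disposition outputs still show them.
- The number may be small. Hypoglycemia is handled first through dose changes, and Protocol 10.3 treats permanent discontinuation as a last resort.
- Safety analyses are descriptive, so no confirmatory conclusion depends on this table.
- SAP Appendix C and the eCRF were not available for this check, so the absence of a hypoglycemia discontinuation table is established only for the text that was.

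**Conclusion.** The point holds as a gap in the recording rule. Following both documents as written, a non-serious symptomatic hypoglycemia that ends treatment need not appear on the AE form, and the by-arm AE-discontinuation figure may undercount such events. The size is 0.4 points of the FRC percentage per omitted patient. The total cannot be derived and could be zero.

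Three stronger inferences are not supported:

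- **That the omission is confined to FRC.** The rule applies to both arms, and control patients may receive basal insulin as rescue (Protocol 8.2.3). It is plausible that FRC would be affected more, because it contains insulin titrated to a fasting target from the start, whereas rescue in control is tied to HbA1c at Week 12 or later.
- **That the table is bound to conflict with the disposition outputs, including the due-to-AE curve.** SAP 2.2 does not name that curve's data source, and SAP 2.5.3 cites the treatment-status page for dates of last administration. Disagreement is possible, not certain.
- **That a given share of FRC discontinuations would be lost.** No discontinuation rate, overall or for hypoglycemia, is given from which to calculate one.

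The conclusion assumes that sites follow the form instructions literally and that the TEAE tables are built from AE records.

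**What to change.** - **Protocol 10.4.2 and 10.6.1:** add one sentence stating that any symptomatic hypoglycemia leading to permanent discontinuation of study drug is also recorded on the AE form, whether or not it is serious.
- **SAP 2.4.5.2:** state that these events count in the overview line and in the table of TEAEs leading to discontinuation, and that the table is reconciled with the disposition reasons before database lock.

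This is a rule for data capture and reporting, and it leaves the management of hypoglycemia untouched. The cost is one sentence in the protocol, a short addition to the SAP, a small reconciliation task, and possibly a slightly less favourable FRC discontinuation figure.

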10.6.2 Local tolerability at injection site

In case the Investigator or the patient recognizes any signs of local intolerance at injection site this should be recorded on the standard AE page in the e-CRF.

10.6.3 Allergic or allergic-like reaction

In case a patient experiences an allergic reaction or an allergic-like reaction this has to be reported as an adverse event and recorded in the e-CRF on the specific AE form for suspected allergic event. Additional information is collected on specific allergic reaction complementary form. Allergic reaction or possible allergic reaction will be adjudicated by the ARAC ([Section 6.4.2](#)).

Virtually all symptoms listed on the allergic reaction complementary form are possible adverse reactions that may be allergic in nature and may need to be addressed after medical judgment, excluding another etiology than allergy.

Sometimes transient injection site reactions, irritant in nature, may occur requiring no intervention and are of dubious significance. These reactions would not be considered to be allergic reactions. Adverse events that are obviously not of allergic origin (eg, local injection site reactions) should not be recorded on the Allergic Event page or Allergic Reaction Complementary Form.

